#### 4.5 Analysis Sets

A summary of the number of patients included in each analysis population described below will be provided. Percentage of patients in the evaluable set will be calculated based on the full analysis set (FAS).

A listing of patients included into each of the analysis set will be presented will be provided. The patients who did not meet the eligibility criteria or were screen failures will also be listed.

- **Full analysis set (FAS)/Safety analysis set:** All patients who were enrolled and received at least one dose of study drug (RXC004).
- CCI  
CCI  
CCI  
CCI  
CCI  
CCI  
CCI
- **PK analysis set:** All patients in the safety analysis set who have had at least 1 blood sample.

#### 4.6 Demographics and Baseline Characteristics

Demographic and Baseline characteristics will be summarized and listed for the FAS.

The following demographic variables will be described:

- Age (years)
- Gender (male or female)
- Race (American Indian or Alaska Native, Asian, Black or African American, Native Hawaiian or Other Pacific Islander, White, Other)
- Ethnicity (Hispanic or Latino, Not Hispanic or Latino, Not Stated, Unknown)

The following baseline characteristic variables will be described:

- Weight (kg)
- Height (only screening visit) (cm)
- Body mass index (BMI) (kg/m^2)
- ECOG Performance Status at Study Entry (Modules 2&3 only)
- Karnofsky Performance Status at Study Entry (Module 1 only)
- Albumin at Study Entry
- Stage at Study entry
- Primary Location
- Cancer Classification (Histology)
- Histological Grade
- TNM Status
- RNF43 Status (Module 1 only)
- PD-L1 Tumor Proportion Score: as continuous and categorical variable (< 1%, ≥ 1% - 49%, > 50%)
- PD-L1 Immune Proportion Score: as continuous and categorical variable (< 1%, ≥ 1% - 49%, > 50%)
- Site of Local/Metastatic Disease (as per extent of disease form)
- Number of Prior Lines of Cancer Therapy
- Best Response Achieved for the Most Recent Treatment Prior to Study Entry
- Time from last Disease Progression disease to first dose of Study Drug (weeks)\*
- Time from Initial Metastatic Diagnosis to first dose of Study Drug (Months)\*

- Time from last most recent Dose of prior therapy to first dose of Study Drug (weeks)\*
- Sum of target lesions at Baseline

(\*) In case, last disease progression date, initial metastatic diagnosis date or most recent dose prior therapy date is incomplete, the following imputation rules will be implemented:

- UK-MMM-YYYY: Assume 01-MMM-YYYY.
- UK-UKN-YYYY: If the year is prior to the year of first dose of study drug, assume 01-JUL-YYYY of the collected year. Otherwise, no imputation.
- UK-UKN- UNKN: No imputation. Duration will be considered as missing.

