5.2 Module 1 (PDAC) Specific Inclusion Criteria

Participants are eligible to be included in Module 1 if in addition to the Core Inclusion Criteria all of the following criteria apply:

8. Histological documentation of advanced (unresectable)/metastatic (Stage III/IV) pancreatic ductal adenocarcinoma, with documented loss of function tumour mutation in RNF43 from centralised genetic pre-screening activities or from a recognised panel in agreement with sponsor*. Please see Section 5.8 and Appendix F for more details.
*

9. Patients must have received one prior systemic treatment for advanced (unresectable)/metastatic pancreatic ductal adenocarcinoma (Stage III/IV), with clear evidence of radiological disease progression. Patients with advanced disease may also have received prior adjuvant therapy. Patients that have radiologically progressed during or within 6 months of completion of systemic adjuvant chemotherapy may also be allowed (as progression within 6 months of adjuvant treatment may be considered as first-line chemotherapy for metastatic disease).
10. Patients must be enrolled and receive first dose of study treatment within 6 weeks of radiologically confirmed progression. In exceptional circumstances, Sponsor approval for patients to be enrolled within 8 weeks of radiologically confirmed progression may be given (exceptional circumstances may include logistical reasons or patients with indolent, oligometastatic disease).
11. Karnofsky performance status ≥ 70 with no deterioration in the 2 weeks prior to first dose and an estimated life expectancy of greater than 12 weeks (See Appendix G).

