5.3 Module 2 and Module 3 (BTC) Specific Inclusion Criteria

Participants are eligible to be included in Module 2 or Module 3 if in addition to the Core Inclusion Criteria all of the following criteria apply:

12. Histological documentation of advanced (unresectable)/metastatic (Stage III/IV) BTC (intrahepatic or extrahepatic cholangiocarcinoma, ampulla of Vater, or gallbladder cancer).
13. Patients must have received one prior systemic treatment for advanced (unresectable)/metastatic Biliary Tract Cancer (BTC), with clear evidence of radiological disease progression (these patients are allowed to have received prior immunotherapy). Patients may also have received prior adjuvant therapy, and additionally, patients that have radiologically progressed during or within 6 months of completion of systemic adjuvant chemotherapy may also be allowed (as progression within 6 months of adjuvant treatment may be considered as first-line chemotherapy for unresectable/metastatic disease).
14. Patients must be enrolled and receive first dose of study treatment within 6 weeks of radiologically confirmed progression. In exceptional circumstances, Sponsor approval

for patients to be enrolled within 7 weeks of radiologically confirmed progression may be given (exceptional circumstances may include logistical reasons or patients with indolent, oligometastatic disease).

15. ECOG status 0 or 1 with no deterioration in the 2 weeks prior to study day 1 and an estimated life expectancy of greater than 12 weeks (See Appendix G).

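### SAP 4.6 turns a year-only progression date from the year before first dose into an interval of at least 26.3 weeks, which no eligible patient can have, and its first-of-month rule only ever lengthens the short intervals

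*SAP*

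**What the plan says.** SAP 4.6 (Demographics and Baseline Characteristics) summarises and lists three intervals for the full analysis set: last progression to first dose (weeks), initial metastatic diagnosis to first dose (months), and most recent prior-therapy dose to first dose (weeks). All three share one set of rules, which apply "In case, last disease progression date, initial metastatic diagnosis date or most recent dose prior therapy date is incomplete":

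- Day missing: "UK-MMM-YYYY: Assume 01-MMM-YYYY".
- Day and month missing: "If the year is prior to the year of first dose of study drug, assume 01-JUL-YYYY of the collected year. Otherwise, no imputation".
- Whole date missing: "UK-UKN- UNKN: No imputation. Duration will be considered as missing".

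No branch checks the imputed date against any other date in the record apart from the year of first dose.

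One of these intervals is limited by eligibility. Protocol 5.3 (inclusion 14, Modules 2 and 3) states: "Patients must be enrolled and receive first dose of study treatment within 6 weeks of radiologically confirmed progression". Protocol 5.2 (inclusion 10, Module 1) sets the same limit. The exceptions differ. In Module 1, "Sponsor approval for patients to be enrolled within 8 weeks of radiologically confirmed progression may be given"; in Modules 2 and 3 the exception goes to 7 weeks.

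**The concern.** The rule suits initial metastatic diagnosis, which may lie years back, so that a mid-year guess is a small relative error. It does not suit an interval that eligibility holds to 6 weeks. A year-only progression date is imputed only when its year precedes the year of first dose. An eligible patient in that position progressed in November or December and was dosed in January or February, yet the rule places progression on 1 July. For this variable, the branch produces a value only where that value must be wrong for an eligible patient.

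The day-missing branch has a milder fault. The first of the month can never be later than the true date, so the error always runs one way, on intervals short enough for a few weeks to matter.

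At stake is the accuracy of two baseline descriptors in single-arm modules that are judged against external benchmarks. A listed interval could also appear to conflict with inclusion 10 or 14.

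**Working it through.** The plan states no figure that depends on this rule, so there is nothing to reproduce. The check is calendar arithmetic. The inputs are the rules in SAP 4.6 and the limits in protocol 5.2 and 5.3 (42 days; 49 or 56 by exception). Two readings are assumed: that last progression in the SAP is the same event as radiologically confirmed progression in the protocol, and that the exception limits run to first dose.

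**Year-only date, calendar year before first dose**

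Imputed interval = first dose − 1 July of the previous year.

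- Shortest: first dose on 1 January gives 184 days, and 184/7 = 26.3 weeks.
- Longest for an eligible patient: progression on 31 December and dosing at the limit.

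| Limit | Latest first dose | Imputed days | Imputed weeks |
|---|---|---|---|
| 6 weeks | 11 February | 184 + 41 = 225 | 32.1 |
| 7 weeks | 18 February | 184 + 48 = 232 | 33.1 |
| 8 weeks | 25 February | 184 + 55 = 239 | 34.1 |

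Overstatement = true progression date − 1 July.

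- It is smallest when progression is as early as eligibility allows for a 1 January dose: 184 − 42 = 142 days (20.3 weeks) under the 6-week limit, or 184 − 56 = 128 days (18.3 weeks) under the 8-week exception.
- It is largest for progression on 31 December: 183 days (26.1 weeks).

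Enumerating every progression date in 2021 to 2024 (years chosen for illustration) with every whole-day gap up to the limit gives the same extremes. If dates and gaps are uniform, the year boundary falls between progression and first dose in 5.7%, 6.7% and 7.7% of pairs under the 6-, 7- and 8-week limits. The month must also be missing for the rule to act.

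**Day missing**

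Overstatement = day of month − 1, so 0 to 30 days. Over a 365-day year the mean is [7 × (31×30/2) + 4 × (30×29/2) + 28×27/2]/365 = (3255 + 1740 + 378)/365 = 14.7 days.

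The largest imputed interval for an eligible patient is 42 + 30 = 72 days (10.3 weeks), or 79 days (11.3 weeks) and 86 days (12.3 weeks) under the exceptions.

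Example: progression on 28 March and first dose on 25 April is 28 days, or 4.0 weeks. Imputed from 1 March it is 55 days, or 7.9 weeks.

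The share of eligible day-missing patients who would appear to exceed their limit depends on the assumed gaps. With gaps uniform from zero it is 34%, 29% and 26% under the 6-, 7- and 8-week limits. Under the 6-week limit it is 41% for gaps of 7 to 42 days and 62% for 21 to 42 days. These are illustrations, since the documents do not give the distribution.

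**Day 15 instead of day 1**

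Error = day of month − 15, so −14 to +16 days, with mean 14.7 − 14 = 0.7 days before any limit at first dose. In the same illustration under the 6-week limit, the share over 42 days falls from 41% to 12% (gaps 7 to 42 days) and from 34% to 10% (gaps 0 to 42 days).

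**The case against.** The strongest reply is that the 1 July branch should be nearly empty. Protocol 8 requires eligibility to be confirmed from completed screening evaluations, and protocol 5 bars waivers. A site that knows only the year of progression cannot show that inclusion 10 or 14 is met. The documents do not show whether the eCRF accepts a partial date, and they give no count of incomplete dates. This stands, and it limits the weight of the point. It does not defend a rule whose only output for this variable is wrong for eligible patients.

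Three stronger readings are tempting, and the documents do not support them.

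- A reader might infer that both branches return 26 weeks or more. Only the 1 July branch does. The first-of-month branch stops at 10.3 weeks (12.3 under the 8-week exception), and same-year year-only dates and wholly missing dates are not imputed.
- A reader might infer that eligible patients would be recorded as protocol violators. SAP 4.4.1 assesses deviations in review meetings against a separate specification, and SAP 4.2.5 reports raw data as provided. An imputed interval could look odd beside these outputs, but it does not drive them.
- A reader might infer that efficacy conclusions are affected. These intervals enter no model (SAP 4.11.1.2), no subgroup (4.11.1.6) and no go/no-go threshold (4.15).

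A long interval is also impossible only for a patient who met the criterion. The full analysis set is everyone enrolled and dosed, and SAP 4.4.1 allows for eligibility violations.

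Finally, day 1 is a common convention, and SAP 4.8 uses it for medication start dates. There, however, it is adjusted when the month and year match those of first dose. Section 4.6 has no such adjustment.

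**Conclusion.** The point holds as a minor defect in a descriptive rule. For a year-only progression date in the calendar year before first dose, the imputed interval is always at least 26.3 weeks, against a limit of 6 weeks (7 or 8 by exception), and it overstates an eligible patient's true interval by at least 18.3 weeks. That result needs only the calendar and the two readings stated above. The one-directional error of 0 to 30 days in the day-missing branch is equally firm, and it applies to time since last prior therapy as well. The shares of patients who would appear to exceed the limit rest on assumed uniform gaps and should not be quoted as expectations.

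The number of patients affected is unknown and probably small. The consequence is limited to baseline summaries and listings. A single value of 26 weeks would mainly distort the mean and the maximum.

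**What to change.** In SAP 4.6:

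1. For last progression, do not impute a year-only date. Leave the interval missing and query the date, which the site needs for eligibility in any case. This agrees with the default in SAP 4.2.8 of no imputation unless otherwise stated.
2. For last progression and last prior-therapy dose with only the day missing, impute the 15th, and no later than the day before first dose.
3. Flag imputed values in the listing.

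Keep the present year-only rule for initial metastatic diagnosis and for last prior-therapy dose. The protocol sets no maximum for time since prior therapy, only a 3-week minimum (core exclusion 6), so a 1 July value can be plausible there. Do not force imputed progression dates into the eligibility window, because that would make a real violator with a partial date look compliant.

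The cost is a few lines of SAP text and a few progression intervals reported as missing. Day 15 remains a guess and can shorten an interval as well as lengthen it, but its average error is close to zero.

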#### 4.7 Medical History and Surgical History

Medical history and Surgical history as pre-specified in the Medical and Surgical history eCRF will be presented in the patient data listings.

#### 4.8 Prior and Concomitant Medications

Prior and concomitant medications will be coded using the World Health Organization - Drug Dictionary (WHO-DD) Version March 2023 and will be classified by Anatomical Therapeutic Chemical (ATC) categories. Prior medications will be defined as medications that stopped before the first dose of study drug and will be listed only.

For the purpose of categorizing medications as prior or concomitant, incomplete medication start and stop dates will be imputed as follows:

Missing start dates (where UK, UKN and UNKN indicate unknown or missing day, month, and year respectively):

- UK-MMM-YYYY: Assume 01-MMM-YYYY. If the month and year are the same as the first dose of study drug month and year, then assume the date of first dose of study drug;
- UK-UKN-YYYY:
  - If the year is prior to the year of first dose of study drug, assume 01-JUL-YYYY of the collected year. If the end date is before 01-JUL-YYYY, assume the first day of the year.
  - If the year is the same as the first dose of study drug year, then assume the date of first dose of study drug. If the End Date occurs before the first dose of study drug, then assume the first day of the year.

- If the year is after the first dose of study drug year, then assume the first day of the year.

UK-UKN- UNKN: Assume date of first dose of study drug. In case end date is before first dose of study drug, assume the first day of the year of the CM end date.

Missing stop dates for concomitant medications data will be handled as follows (where UK, UKN and UNKN indicate unknown or missing day, month, and year respectively):

- UK-MMM-YYYY: Assume the last day of the month;
- UK-UKN-YYYY: Assume 31-DEC-YYYY;
- UK-UKN- UNKN: Assume ongoing and leave it missing.

Medications will be categorized as follows:

Medication start and stop dates will be compared to the date of first dose of study medication to allow medications to be classified as either Prior or Concomitant.

Medications and treatments administered prior to the investigational medicinal product (IMP) intake which stopped prior to IMP intake will be considered as prior medications. Medications and treatments which started before, on or after the IMP intake and which stopped after IMP intake of study drug (including medications and treatments which stopped the day of the IMP intake) will be considered as concomitant medications. If medication start and/or stop dates are missing or partial, the dates will be compared as far as possible with the date of IMP dosing. Medications will be assumed to be concomitant, unless there is clear evidence (through comparison of partial dates using the rules above) to suggest that the medication stopped prior to the IMP dosing. If there is clear evidence to suggest that the medication stopped prior to the IMP dosing, the medication will be assumed to be Prior.

Medications and treatments with a start date after the last dose of IMP will be considered as Post-study medication and will not be considered as concomitant medications.

Concomitant medications will be analysed for the FAS.

The number (n) and percentage (%) of patients taking concomitant medications will be summarized by ATC classification and Preferred Name. ATC Level 1 will be sorted by alphabetical order. Preferred Names, within each ATC Level 1, will be sorted by descending frequency of the total frequency. In the event of Preferred Names with equal total frequencies, the relevant Preferred Names will be sorted alphabetically. Similarly, if a patient reported more than one concomitant or post-treatment medication within the same primary ATC Level 1, the patient will be counted only once.

Prior and concomitant medications (ATC Level 1/Preferred Name), dose, frequency and route, start/stop date (or ongoing) and type of indication as specified in the eCRF with medication category (Prior or Concomitant) will be presented in the by- patient data listing for FAS.

Additional summaries and listing will be created specifically for Prior anti-cancer therapies.

#### 4.9 Prior and Concomitant Radiotherapy and Procedure

Prior and concomitant radiotherapy will be summarized and listed for the FAS.

The following prior radiotherapy variables will be described:

- Number of patients having a history of radiotherapy
- Intent of prior radiotherapy
- Sites of prior radiotherapy

The following concomitant radiotherapy variables will be described:

- Number of patients having a concomitant radiotherapy
- Intent of concomitant radiotherapy
- Sites of concomitant radiotherapy

Concomitant procedure will be listed for the FAS.

#### 4.10 Treatment Exposure/Compliance

Treatment Exposure

Duration and compliance of the RXC004 exposure will be assessed by computing the following variables from RXC0004 Drug Administration form:

- Number of cycles and number of doses per patient
- RXC004 Duration of treatment (weeks) = (Date of last dose – Date of first dose + 1) / 7
- Pembrolizumab Duration of treatment (weeks) = (Date of last dose + 42 – Date of first dose) / 7
- Cumulative dose (mg) = Sum of all doses administered
- RXC0004 RDI (%) = [Cumulative dose received (mg) / (RXC004 Duration of treatment (days) \* 2mg)] \* 100, for Module 1&2
- RXC0004 RDI (%)= [Cumulative dose received (mg) / (RXC004 Duration of treatment (days) \* 1.5mg)] \* 100, for Module 3

- Pembrolizumab RDI (%) = [(Cumulative dose received (mg) \* 6 (weeks)) / (Pembrolizumab Duration of treatment (weeks) \* 400 (mg))] \* 100, for Module 3
- Number of patients with dose reduced and reason for reduction
- Number of patients with dose interrupted and reason for interruption

Duration of the RXC004 duration, and Cumulative dose will be summarized as continuous variables. RDI will be summarized as continuous variable and by categories: [0%; 60% [, [60%; 75% [, [75%; 90% [, [90%; 100% ], ]100%; + ]].

The number of patients who had dose reductions will be summarized by categories: (Any, 1, 2 times).

Another summary will be produced excluding treatment cycles after the progression for the patients who remain on treatment despite PD. A swimmer plot will be produced presenting the duration of treatment. Some tags will show the RECIST assessment responses (CR, PR, SD, PD) along the study.

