8.5.1 Pharmacokinetics

Venous blood samples (2 mL) for determination of concentrations of RXC004 in plasma, this may also permit investigation of any significant metabolites. Samples will be taken after a single dose of RXC004 in Cycle 0 Day 1 at designated times (Table 15, Table 16, and Table 18) up to 48 h post-dose and again at Cycle 1 Day 15 at designated times up to 24 h post-dose. Cycle 0 may be 3-7 days in duration to allow for flexibility in scheduling the full PK time course at Cycle 1 Day 15 to avoid weekend sampling if required. CCI

CCI if required. The date and time that the last dose of RXC004 was administered prior to Cycle 1 Day 15 and the date and time of collection of each sample will be recorded.

The timing of the PK samples may be adjusted during the study, dependent on emerging data, in order to ensure appropriate characterisation of the plasma concentration-time profiles. The total number of samples and the total volume of blood taken from each patient will not exceed that outlined in the Lab Manual.

If a patient misses any doses of RXC004 within 3 days of PK sampling, please contact the Sponsor representative as to any effect on the changes required on the timing of the PK assessments. All other assessments, including laboratory safety assessments, vital signs and RECIST should continue to be performed as per study plan, relative to baseline assessments.

Samples will be collected, labelled, stored and shipped as detailed in the Laboratory Manual.

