Vitamin D3 and Calcium supplements						Patients should commence 800 IU vitamin D3 (Cholecalciferol) QD and 1000-1500 mg calcium daily supplements from ICF signature until RXC004 discontinuation	

Module 1 (PDAC)– Schedule of assessments							
	Pre-Screening ^t	Screening	Cycle 0 (3-7 days)	Cycle 1 (21-day cycle)	Cycle X Day (21-day cycle)	IP	30 day follow-up
Window	n/a	-28 to -1	D1	D1 ± 1d	± 3d	Within 7 days of discontinuation	± 3d
Denosumab dosing ^g				120 mg SC denosumab once every month from C0D1 until RXC004 discontinuation			q6w ± 1 week
RXC004 dosing ^y			X (2mg single dose)	Continuous daily dosing (2mg QD)			
RXC004 diary			X		Review at each visit	X	
Concomitant medication		X	X	X	X	X	X
Adverse events		X	X	X	X	X	X
Taste assessment ^s		X			At each visit - only if patient reports dysgeusia		
Survival status and post-discontinuation anti-cancer therapy ^h						X	X

^a Screening (pre-first dose IP) biopsy is a mandatory requirement except in exceptional circumstances in which biopsy is not technically feasible. All patients without a baseline sample must be approved by the Sponsor before starting study treatment. The baseline **CCI** can be a 'fresh newly acquired' biopsy or an **CCI** (from the same site that 'on treatment' biopsy will be taken) and taken after completion of all prior standard of care treatments. In exceptional circumstances where baseline biopsy cannot be scheduled before C0D1, the procedure may be performed before C1D1 after a minimum of 4 days washout from C0D1. A second 'on treatment' biopsy at C1D15 (+ up to 7 days), is also mandatory providing that investigator judges the second biopsy to be technically and clinically feasible. An optional biopsy at progression is encouraged. The Cycle 1 Day 15 biopsy should be collected post-dose and the time of collection should be accurately recorded. RECIST 1.1 target lesions should not be chosen for biopsies.

^b **CCI**
^c **CCI**
^d **CCI**
^e **CCI**
^f Blood samples for PK analysis should be collected as follows (the actual time for each blood draw must be accurately recorded):

Cycle 0: CCI	CCI
Cycle 1, CCI	CCI
Cycle X, CCI	CCI

^g **CCI**

^h Survival and details of first and subsequent therapies for cancer, after discontinuation of treatment, will be collected

ⁱ CT (preferred) or MRI, each preferably with IV contrast. It is strongly recommended to maintain use of the same imaging modality (CT or MRI), acquisition protocol, facility, scanner and

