RXC004 dosing ^t		X (2mg single dose in Cohort 1; 1mg single dose in Cohort 2)		Continuous daily dosing (2mg QD in Cohort 1; 1mg QD in Cohort 2)			
RXC004 diary		X			Review at each visit	X	
RXC004 PK ^f		X		X	X		
Concomitant medication	X	X	X	X	X	X	
Adverse events	X	X	X	X	X	X	
Taste assessment ^s	X			At each visit – only if patient reports dysgeusia			
Survival status and post-discontinuation anti-cancer therapy ^g					X	X	

^a Screening (pre-first dose IP) biopsy is a mandatory requirement except in exceptional circumstances where biopsy is not technically feasible. All patients without a baseline sample must be approved by the Sponsor before starting study treatment. The baseline **CCI** can be a 'fresh' newly acquired' biopsy or an **CCI** (from the same site that 'on treatment' biopsy will be taken) and taken after completion of all prior standard of care treatments. In exceptional circumstances where baseline biopsy cannot be scheduled before C0D1, the procedure may be performed before C1D1 after a minimum of 4 days washout from C0D1. A second 'on treatment' biopsy at C1D15 (± up to 7 days), is also mandatory providing that investigator judges the second biopsy to be technically and clinically feasible. An optional biopsy at progression is encouraged. The Cycle 1 Day 15 biopsy should be collected post-dose and the time of collection should be accurately recorded. RECIST 1.1 target lesions should not be chosen for biopsies.

^b **CCI**
^c **CCI**
^d **CCI**

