### 4.2.1 Study Days

Screening will be conducted between Day -28 and Day -1. The first day of treatment will be Cycle 0 - Day 1 (C0D1). When calculating AEs/ConMeds/etc timing days will be calculated relative to Day 1.

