### 4.2.2 Visit Windowing

By visit summaries will be made considering the windows as below. The visit windowing is assessed relative to C1D1 date (not C0D1 due to delays between C0D1 and C1D1).

C0D1	C0D1
C1D1	(C1D1 - Day 8)
Day 15	(Day 9 - day 18)
Day 22	(Day 19 - Day 32)
Day 43	(Day 33 - Day 53)
Day 64	(Day 54 - Day 74)
Day 85	(Day 75 - Day 95)
Day 106	(Day 96 - Day 116)
Day 127	(Day 117 - Day 137)
Day 148	(Day 138 - Day 158)
Day 169	(Day 159 - Day 179)
Day 190	(Day 180 - Day 200)
Day 211	(Day 201 - Day 221)
Day 232	(Day 222 - Day 242)
Day 253	(Day 243 - Day 263)
Day 274	(Day 264 - Day 284)
Day 295	(Day 285 - Day 305)
Day 316	(Day 306 - Day 326)
Day 337	(Day 327 - Day 347)
Day 358	(Day 348 - Day 368)

The following visits will not be remapped: Screening, IP Discontinuation, 30/90 Day Follow-up, Survival Follow-up.

In case several visits occur into the same windows the following rule is to be applied:

- For by-visit table, we will consider the mean of available assessments.
- For Shift table, we will consider either Minimum or Maximum available value depending on the direction.

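### SAP 4.10 counts planned dose-free Cycle 0 days in the RXC004 relative dose intensity and, if Module 2 Cohort 2 enrolled, divides its 1 mg dosing by 2 mg

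*SAP*

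**What the plan says.** SAP 4.10 gives "RXC0004 RDI (%) = [Cumulative dose received (mg) / (RXC004 Duration of treatment (days" times 2 mg for Modules 1 and 2 together. A second formula uses 1.5 mg for Module 3. Duration is "RXC004 Duration of treatment (weeks) = (Date of last dose – Date of first dose + 1) / 7", and SAP 4.2.1 fixes the start: "The first day of treatment will be Cycle 0 - Day 1 (C0D1"). RDI is reported as a continuous variable and in five bands: below 60%, 60 to below 75%, 75 to below 90%, 90 to 100%, and above 100%.

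The protocol gives the dosing that RDI should be measured against. Section 8.5.1 says "Samples will be taken after a single dose of RXC004 in Cycle 0 Day 1" and "Cycle 0 may be 3-7 days in duration to allow for flexibility". The Module 1 schedule (Table 15) enters Cycle 0 dosing as "X (2mg single dose"). The Module 2 schedule (Table 16) has "X (2mg single dose in Cohort 1; 1mg single dose in Cohort 2"). Table 18 has one 1.5 mg dose in Cycle 0 for Module 3. In all three schedules daily dosing follows Cycle 0.

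Protocol Tables 10 and 16 assign Module 2 Cohort 2 to 1 mg once daily. Sections 4.4.1.6 and 11.5 make the opening of that cohort depend on the Cohort 1 data.

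**The concern.** RDI compares dose received with dose planned, so a patient who follows the schedule exactly should score 100%. The SAP formula does not give this, for two reasons.

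- **All modules.** The denominator treats every calendar day from C0D1 as a dosing day. The rest of Cycle 0 after the single dose is dose-free by design, and the formula counts those days as missed treatment.
- **Module 2 Cohort 2, if it enrolled.** The denominator uses 2 mg for patients assigned 1 mg.

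Nothing else in the SAP adjusts for either point. The pembrolizumab formula in the same section does follow its schedule. With n doses given 42 days apart, duration is 6n weeks and RDI is (400n x 6)/(6n x 400) = 100%.

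What is at stake is a table that understates adherence to RXC004. In Cohort 2, which was meant to inform on the tolerability of a lower dose, it would halve it.

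**Working it through.** The documents state no RDI value, so there is no figure to reproduce. The SAP formula is applied directly.

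**Inputs.** T = last dose date - C0D1 date + 1 (SAP 4.10). k = days from C0D1 to C1D1, planned as 3 to 7 (protocol 8.5.1 and the schedules). Cycle 0 has one dose, then daily dosing. It is assumed that a Cycle 0 of k days has k - 1 dose-free days, that is, 2 to 6.

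**1. Fully dosed patient, correct mg.** Doses taken = 1 + (T - k), so SAP RDI = (T - k + 1)/T. It reaches 90% when T is at least 10(k - 1), which is 20, 30, 40, 50 and 60 days for k = 3 to 7.

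| T (days) | k = 3 | k = 7 |
|---|---|---|
| 14 | 12/14 = 85.7% | 8/14 = 57.1% |
| 28 | 26/28 = 92.9% | 22/28 = 78.6% |
| 42 | 40/42 = 95.2% | 36/42 = 85.7% |
| 49 | 47/49 = 95.9% | 43/49 = 87.8% |
| 60 | 58/60 = 96.7% | 54/60 = 90.0% |
| 180 | 178/180 = 98.9% | 174/180 = 96.7% |

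The correct value in every cell is 100%. With k = 7 this patient is placed below 60% for T = 8-14, in 60 to below 75% for T = 15-23, in 75 to below 90% for T = 24-59, and in the right band from T = 60. With k = 3 the corresponding values are T = 4, 5-7, 8-19 and from 20.

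Short exposure is realistic: protocol 4.4.1.6 puts median Phase 1 exposure at about 7 weeks (T = 49).

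**2. Patients not fully dosed.** For anyone who enters Cycle 1, SAP RDI equals planned-day RDI times (T - k + 1)/T, a relative loss of (k - 1)/T. Near a cut-off even a small loss changes the band.

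- Reduction: k = 7, C0D1 dose, 14 days at 2 mg, then 150 days at 1.5 mg. Cumulative dose = 2 + 28 + 225 = 255 mg and T = 7 + 14 + 150 = 171. SAP: 255/(171 x 2) = 255/342 = 74.6%. On planned days: 255/(165 x 2) = 255/330 = 77.3%. The band differs.
- Same pattern with 300 days at 1.5 mg (T = 321): 480/642 = 74.8% against 480/630 = 76.2%. With 600 days (T = 621): 930/1242 = 74.9% against 930/1230 = 75.6%.
- Missed doses: k = 7, T = 175, 169 planned doses, 12 missed. SAP: 157/175 = 89.7%. On planned days: 157/169 = 92.9%. At this T and k, missing 12-16, 38-42 or 65-67 doses changes the band.

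**3. Module 2 Cohort 2, if enrolled.** The fully dosed values are halved: 28.6-42.9% at T = 14, 43.9-48.0% at T = 49 and 48.3-49.4% at T = 180 (k = 7 to k = 3). With the C0D1 dose only, RDI is exactly 50%. The patient always falls below 60%.

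**The case against.** The strongest reply is that little depends on this. RDI here is descriptive, and number of doses, cumulative dose, reductions and interruptions are reported beside it. For a fully dosed patient at T = 180 the shortfall is only 1.1 to 3.3 points. This stands, and it limits the severity.

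Cohort 2 may also never have opened. The SAP follows protocol version 6, and its RDI definitions were revised in September 2023, yet its readable text mentions no Module 2 cohorts and no 1 mg dose. Its Module 2 sample-size text also lacks the protocol's per-cohort wording. That fits a plan written for 2 mg patients only. SAP 4.16, however, does not list the cohort as dropped. A reader might infer that Module 2 RDI is certainly wrong on this count. The documents do not support that, so the second fault stays conditional.

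Two other inferences go too far:

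- A reader might conclude from the fully dosed case that no band changes from 60 days on. The reduction example at T = 171 shows otherwise.
- SAP 4.2.2 anchors visit windows to C1D1, "not C0D1 due to delays between C0D1 and C1D1". A reader might take this as evidence that Cycle 0 is expected to exceed 7 days. The phrase fits the ordinary 3 to 7 day gap equally well, and no passage reports a longer one.

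**Conclusion.** The RXC004 RDI denominator is wrong as written, and the severity is minor. The Cycle 0 fault applies in every module and lowers the RDI of every patient who enters Cycle 1 by a relative (k - 1)/T. For a fully dosed patient it changes the band only below 20 days (k = 3) to 60 days (k = 7). For patients with reductions or missed doses near 60, 75 or 90%, it can change the band at any exposure length. The Cohort 2 fault is a constant factor of two and matters only if that cohort enrolled.

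The result assumes that RDI is meant as received over planned dose, and that the days in the RDI formula are the calendar days in the duration definition. A reader might suspect a wider effect, but RDI does not enter the 6-month PFS rate, the objective response rate or the go/no-go rule.

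**What to change.** Replace both RXC004 formulas in SAP 4.10 with one:

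RDI (%) = 100 x cumulative dose / (protocol-assigned starting dose for the patient's module and cohort x planned dosing days).

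- Patients who reached C1D1: planned dosing days = T - (min(k, 7) - 1).
- Patients with the C0D1 dose only: planned dosing days = 1.

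With k = 3 to 7 this returns 100% for a fully dosed patient at any T, including Cohort 2 at 1 mg.

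The cap at 7 is a convention taken from the protocol's maximum Cycle 0 length, and the SAP should state it as such. It makes any longer gap count as lost dose intensity. For example, k = 10 and T = 42 gives 33 doses and 33/36 = 91.7%, whereas excluding the whole gap would give 100%. The choice matters: allowing only a 3-day Cycle 0 would give 33/40 = 82.5%.

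If Cohort 2 enrolled, report Module 2 RDI by cohort. If it did not, say so in SAP 4.16. The duration-of-treatment variable can stay as it is. The cost is SAP wording and a programming change, using dosing dates already available, with no new data.
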